## 11. Collection of biological material

Volunteers blood samples will be taken at time zero, after 1, 2, 3, 6, 9 and 12 months, after agreement and signature of the ICF. Blood collection will be performed by a specialist in the laboratory of clinical analyzes at predetermined dates immediately after exposure of the patients to the sand. The samples will be transported in an isothermal box with ice to the Vila Velha University laboratory, where they will be immediately frozen at -80°C until analysis.

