## 2. Experimental Protocol

The study will be carried out on the beaches of Areia Preta de Guarapari (source of monazitic sands) and on the beach of Itapoã in Vila Velha (sand without radiation). Selected patients will have their knees fully covered with beach sand, properly analyzed for radioactivity and temperature, for 30 minutes on 2 mornings a week for a period of 1 (one) year.

Patients will be enrolled in relation to age, gender, weight, height and body mass index (BMI). An investigation / monitoring will be performed regarding the current use of medications for disease control and associated comorbidities.

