# 3. The size of the sample

The sample size of the patients was calculated considering the necessary amount of subjects to detect difference of at least 3 points in the pain perception through the visual analgesic scale (scale from 0 to 10), considering a significance level of 1% and test power of 95% in two-tailed hypothesis test, as well as the value of 4 for standard deviation (MATA et al., 2015). The sample was calculated in 126 patients and considering a sample loss around 20%, the number of subjects was 150, with 75 subjects in each sample (BENAZZI, FIGUEIREDO, BANASSI, 2010).

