## 7. Removal criteria

Patients will be removed when:

- Undergoing knee surgery during the course of the research.
- Subjected to joint infiltration with corticoids or any other type and medication of intraarticular use.
- Heat intolerant or other discomfort during exposure to sand.

For evaluation and follow-up of the volunteers will be carried out in parallel a work of pharmaceutical attention with monitoring of the use and frequency of medications, especially the use of analgesics and / or anti-inflammatories.

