#### 9. Intervention

Patients selected for the study will have their knee (s) affected by OA fully submerged in the beach sand 2 (two) times per week for 30 (thirty) minutes each session at the same location and at the same time of day.

The natural gamma (②) radiation doses of the monazite sands will be monitored in both groups through equipment that counts and accumulates the records for the desired time. In addition, the radiation measurements ② will be associated with the atmospheric and climatic measurements of each group. An interview with the patients will be performed initially (Appendix B), blood collected for analysis and applied to the Visual Analogue Scale (Annex C) and WOMAC (Annex D). The questionnaires as well as the blood collection for laboratory analysis will be repeated at the beginning of the study (day zero) and after 1, 2, 3, 6, 9 and 12 months for later analysis and comparison of the data.

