### 10.2 Secondary Outcome Measures:

- Change total score (0 96) the Western Ontario and McMaster Universities
  Osteoarthritis Index (WOMAC)- (lower scores indicate lower levels of symptoms or physical disability)
- Reduction of Nonspecific inflammatory markers: evaluation of nonspecific inflammatory markers (HSV and CRP) and specific (IL-1β, IL-6, IL-8, IL-17, TNF-α and TGF-β)
- Reduction of Self-medication to treat pain

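### Follow-up blood is drawn only after a sand session just completed, and removed patients have no later follow-up, so marker comparisons after stopping cover only patients still in sessions

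*Combined protocol and SAP*

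**What the plan says.** All references are to the combined protocol and SAP.

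- **Section 11** sets the calendar: "Volunteers blood samples will be taken at time zero, after 1, 2, 3, 6, 9 and 12 months". It then times each draw "at predetermined dates immediately after exposure of the patients to the sand". It gives no alternative for a patient who has no session that day.
- **Section 9** gives the same calendar for questionnaires and blood without the exposure condition. It does not say whether patients who have stopped sessions are still sampled.
- **Section 2** schedules the sand "for 30 minutes on 2 mornings a week for a period of 1 (one) year".
- **Section 7** lists three grounds for removal: knee surgery, intra-articular treatment, and "Heat intolerant or other discomfort during exposure to sand". It describes no data collection after removal. Its paragraph on medication monitoring speaks of the volunteers in general and does not mention those removed.
- **Section 10.2** makes reduction of the inflammatory markers a secondary outcome. There are eight: ESR (printed there as HSV; section 12.1 names the test), CRP and six cytokines.
- **Section 14** names the tests and the significance threshold. It gives no analysis set and no rule for missing values.

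**The concern.** A randomised comparison of markers needs values from the patients who were randomised, including those who stopped. Here the draw depends on something that happens after randomisation, namely attending a session that day, and the removal rule stops follow-up for those who leave. The marker data at each later visit then describe patients still in sessions. If those who stop differ between arms in number or in kind, the comparison no longer rests on randomisation, and samples that were never taken cannot be recovered at analysis.

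There is also a question of meaning. A sample taken straight after 30 minutes in the sand reflects both any acute response to that session and any effect built up over months. If staff do sample patients who have stopped, rested samples are mixed with post-session samples, and nothing in the plan requires the difference to be recorded.

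**Working it through.** **Step 1. Apply the draw rule to each type of patient (months 1, 2, 3, 6, 9, 12).**

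| Patient on the draw date | Date condition | Exposure condition | Draw provided for in section 11? |
|---|---|---|---|
| Attends that day's session | met | met | yes |
| Continuing, but misses that day's session | met | not met | no |
| Removed under section 7 | met | not met | no; section 7 has no later follow-up |
| Stopped for another reason | met | not met | no |

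A patient with poor attendance who comes on the draw date is sampled. The comparison is therefore among patients on treatment at the draw, not among those adherent throughout. Values collected before stopping remain usable.

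**Step 2. Reproduce the plan's sample size, which supplies the loss figures.** Inputs from section 3: difference 3, SD 4, two-sided 1%, power 95%.

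n per arm = 2 × [SD × (z for 0.995 + z for 0.95) / difference]² = 2 × [4 × (2.576 + 1.645) / 3]² = 63.3

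The total is 126.7. The plan's 126 follows from rounding down to 63 per arm; rounding up gives 128. The figure is reproduced. It concerns VAS, and is used here only for the allowance for loss:

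- built-in allowance: 150 − 126 = 24 patients (24/150 = 16%);
- stated loss of about 20%: 0.20 × 150 = 30 patients, leaving 120, or 60 per arm if balanced.

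Both are upper figures. Loss includes people who leave altogether and would give no blood under any wording.

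**Step 3. Spread over visits.** The documents give no timing of loss. If it were even over 12 months (an assumption), the number without a marker value at month m is total × m/12:

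| Month | 1 | 2 | 3 | 6 | 9 | 12 |
|---|---|---|---|---|---|---|
| Total 24 | 2 | 4 | 6 | 12 | 18 | 24 |
| Total 30 | 2.5 | 5 | 7.5 | 15 | 22.5 | 30 |

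**Step 4. When does this bias the comparison?** Assume no true effect. In each arm a fraction s stops, and those who stop differ from those who continue by D (in SD units). If the arm's overall mean is 0, the mean among continuers is −s × D. The false difference between arms A and B is then s_B × D_B − s_A × D_A. With assumed values, none of them from the documents, and the same D in both arms:

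| Stopping, A vs B | D = 0.5 | D = 1.0 |
|---|---|---|
| 20% vs 20% | 0 | 0 |
| 10% vs 30% | 0.10 SD | 0.20 SD |
| 20% vs 10% | −0.05 SD | −0.10 SD |

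The formula shows that bias needs a difference between arms in s or in D.

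**The case against.** **The removal rule is the main cause.** Section 7 limits data to patients on treatment by itself, and it affects VAS and WOMAC as well. This stands: changing section 11 alone would leave removed patients without follow-up and would contradict section 7. The draw rule still matters, because if section 7 were changed alone, section 11 would still provide no draw for those patients.

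**The phrase may only be a timing instruction for those who attend.** The calendar in section 9, and the predetermined dates in section 11 itself, are compatible with sampling patients who have stopped. So a reader should not infer that the plan forbids such samples. It does not provide for them, and that is enough for the point.

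**A reader might infer that the arms lose different patients**, since heat discomfort is a ground for removal and the arms use different sand. The documents do not support this. Both arms have 30 minutes in beach sand in the morning, section 2 has the sand analysed for temperature, and nothing says that one sand is hotter or less well tolerated.

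**Acute warmth is common to both arms.** Drawing both arms at the same point after a session is a form of standardisation, and an acute effect shared by both would at least partly cancel between arms. That stands. An acute effect that differed between the sands would not cancel, and change within an arm would include it in either case. Section 10.2 asks only for reduction and does not say that it must be sustained, so a reader should not infer that the outcome as defined is violated.

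**A reader might infer that time on ice differs by arm**, because there are two beaches and one receiving university. The documents give no transit time or distance and no clear draw site. Section 11 refers to the clinical analysis laboratory, and section 12.1 says it is still to be contracted. The inference has no basis in the text.

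**Conclusion.** The point holds in a limited form. Sections 7 and 11 together restrict marker values after stopping to patients in a session on the draw date, and nothing in sections 9 or 14 repairs this. Post-session samples also leave acute and sustained effects unseparated.

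The reach is all eight markers at the draws after a patient stops, for at most about 24 to 30 of 150 patients by month 12. Those figures assume that the plan's own loss allowance consists entirely of patients who could otherwise have been sampled. Neither the presence nor the size of bias can be established from the documents; the SD figures above only illustrate the mechanism. The draw rule affects secondary outcomes only. The change is worth making before follow-up, because the rule as written yields a weaker comparison than one that uses the same visits.

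**What to change.** Three linked changes, to be made together:

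1. **Section 11.** Replace "at predetermined dates immediately after exposure of the patients to the sand" with: *on the predetermined date counted from randomisation, before any sand session that day, in all randomised patients who still consent, whether or not they still attend sessions*. Record the time since last exposure with each sample.
2. **Section 7.** State that stopping sessions does not end the scheduled blood draws and questionnaires. The grounds for ending sessions are not touched.
3. **Section 14.** State that these values are analysed in the group to which the patient was randomised.

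The cost is small. Patients who have stopped attend draws already on the schedule, attending patients give blood before rather than after the session, and one data item is added. Section 9 keeps sessions at the same time of day, so on session days the draw has to be fitted in ahead of that time. No common draw site for the two arms is needed.

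### Cytokine samples are frozen only on arrival in the control arm's town, with no common handling time, so draw-to-freezer delay may differ by arm and bias these secondary comparisons

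*Combined protocol and SAP*

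**What the plan says.** All references are to the combined protocol and SAP.

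- **Sites.** Section 2 names the "beaches of Areia Preta de Guarapari (source of monazitic sands) and on the beach of Itapoã in Vila Velha (sand without radiation"). Section 9 has patients attend "each session at the same location and at the same time of day". Each sand, and so each arm, is tied to one town.
- **Draw.** Section 11 lists time zero and months 1, 2, 3, 6, 9 and 12, and puts collection "at predetermined dates immediately after exposure of the patients to the sand". On who draws, and possibly where, it says: "Blood collection will be performed by a specialist in the laboratory of clinical analyzes". This can mean that the draw takes place in a laboratory, or only that the specialist belongs to one.
- **Transport and freezing.** Section 11 goes on: "The samples will be transported in an isothermal box with ice to the Vila Velha University laboratory". Freezing is described only for that destination: "where they will be immediately frozen at -80°C until analysis".
- **Assays.** Section 12.1 gives the hemogram, CRP and sedimentation rate to a contracted laboratory with no stated location. Section 12.2 measures the cytokines in serum, in partnership with a university immunology laboratory.
- **Outcome and test.** Section 10.2 lists the markers, "specific (IL-1β, IL-6, IL-8, IL-17, TNF-α and TGF-β") among them, as secondary outcomes worded as a reduction. Section 14 names the tests and the 0.05 threshold, but not whether levels or changes are compared.

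The plan gives no maximum time from draw to centrifugation or freezing, no recording of those times, no statement of when serum is separated, and no step that makes handling alike in the two arms.

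**The concern.** Arm and town coincide, and the freezer is in the control arm's town. If blood is drawn at the beach, as a draw immediately after exposure suggests, Guarapari samples probably spend longer on ice than Vila Velha samples. Where a cytokine concentration changes while the sample waits, the extra wait shifts one arm and not the other. A comparison of follow-up levels cannot tell that shift from a treatment effect. It could look like an anti-inflammatory effect of monazite sand, or hide one.

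The laboratory markers are also the efficacy outcomes that do not rest on patient report. Pain, WOMAC and self-medication do, and patients can hardly fail to know which beach they attend. If handling times are not recorded at collection, the question cannot be settled afterwards.

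**Working it through.** **Step 1. Passages side by side.** Sections 2 and 9 tie arm to town. Section 11 puts the freezer in Vila Velha and freezes only on arrival. No section limits, records or equalises the time between. A longer chain for Guarapari samples is therefore a reasonable inference, not a stated fact.

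**Step 2. Inputs.** From the documents: 75 patients per arm (Section 3); 126 before the allowance for loss, so 126/2 = 63 per arm; threshold 0.05 (Section 14). Not in the documents, and assumed below: extra delay, marker drift, between-patient SD, and baseline-to-follow-up correlation. The plan has no figure of its own on this point to reproduce.

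**Step 3. Comparing follow-up levels, no true effect.** An artefact of b SD shifts the test statistic by b/SE, with SE = sqrt(2/n). The false-positive chance is Φ(b/SE − 1.96) + Φ(−b/SE − 1.96). With n = 75, SE = sqrt(2/75) = 0.163.

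| Assumed delay × drift | Assumed SD | b | b/SE | Chance of p<0.05 |
|---|---|---|---|---|
| 0.5 h × 5%/h = 2.5% | 40% of mean | 0.0625 | 0.38 | 6.7% |
| 1.25 h × 10%/h = 12.5% | 40% of mean | 0.3125 | 1.91 | 48% |
| 2.5% | 1 on log scale | ln 1.025 = 0.025 | 0.15 | 5.3% |
| 12.5% | 1 on log scale | ln 1.125 = 0.118 | 0.72 | 11% |

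The result depends almost wholly on the assumed inputs. Changing the SD alone takes the worst case from 48% to 11%.

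**Step 4. Does the baseline sample help?** A simulation used 63 per arm, log SD 1, correlation 0.6 (both assumed), no true effect, and an artefact that multiplies one arm.

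| Multiplier | Levels | Change, same artefact at time zero | Change, no artefact at time zero |
|---|---|---|---|
| 1.1 | 8–9% | 5% | 9% |
| 1.2 | 16–18% | 5% | 21% |
| 1.35 | 38–39% | 5% | 47% |
| 1.65 | 79–80% | 5% | 88% |

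The formula agrees. At 1.35 the shift is ln 1.35 = 0.300. The SD of change is sqrt(2 × (1 − 0.6)) = 0.894 and SE = 0.894 × sqrt(2/63) = 0.159. The ratio is 1.88, which gives 47% when the baseline sample lacks the artefact.

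**Step 5. Change and covariate adjustment differ here.** With equal variances the adjustment slope equals the correlation, 0.6. Adjustment then removes 60% of a constant artefact and leaves 1 − 0.6 = 40%. At 1.35 the remainder is 0.4 × 0.300 = 0.120. The residual SD is sqrt(1 − 0.6²) = 0.8 and SE = 0.8 × sqrt(2/63) = 0.143. The ratio is 0.84, or about 13% false positives: well below the 39% for levels, but not 5%.

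**The case against.** **The text leans towards cancellation.** Section 11 gives one collection and transport description for all draws, time zero included. Section 10.2 words the outcome as a reduction, and Section 1 speaks of paired samples. If baseline blood takes the same route and change is tested, a constant artefact cancels. This stands as the more natural reading, but it is not secured. Section 14 does not name the variable. Section 9 mentions blood at the initial interview and Section 8 recruits at Vila Velha health units, so baseline blood could be drawn there without the Guarapari delay. Delay that varies between visits would not cancel either.

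**The size is assumed.** This stands in full. Nothing in the documents shows that a drift of 5 to 10% per hour applies to samples on ice, or that the samples travel unseparated.

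**Only secondary outcomes are affected.** This also stands; the primary pain outcome and WOMAC are untouched. Arm would remain tied to beach and climate even with matched handling.

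**Details may be in a laboratory manual.** Possibly, but the documents refer to none.

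A reader might also infer four stronger points, none of which the documents support:

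- *All blood goes to one laboratory, so CRP and sedimentation rate are equally affected.* Sections 12.1 and 12.2 name other laboratories, and the route for CRP, sedimentation rate and hemogram is not described.
- *Delay certainly differs by arm, wherever blood is drawn.* No times or distances are given. If the draw is in a laboratory, the arm difference moves to the interval from exposure to draw, and its direction depends on an unknown location.
- *Arm is confounded with assay run.* Samples are stored frozen until analysis, and nothing says they are assayed in order of arrival.
- *No analysis could separate the delay from treatment.* Step 4 shows that change from a same-route baseline removes a constant artefact.

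**Conclusion.** The concern holds in limited form. The plan ties each arm to a town, freezes only on arrival in the control arm's town, and neither equalises nor records the time between. Draw-to-freezer time for the stored cytokine samples may therefore differ systematically by arm and bias these secondary comparisons. The risk is greatest if follow-up levels are compared or if baseline blood is handled differently.

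The documents do not allow the size to be computed. The illustrative range of about 5% to 48% rests on assumed delay, drift and SD, and on comparing levels. With the same artefact at time zero and change analysed, the rate returns to about 5%. The change is worth making because it is cheap and missing times cannot be recovered later. It does not threaten the primary analysis.

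**What to change.** **Section 11.** State the place of draw. Set one draw-to-centrifugation interval and one draw-to-freezing interval for both arms, at a length that Guarapari samples can meet, and hold Vila Velha samples on ice to match. Apply this at time zero and at every later visit. Record draw, centrifugation and freezing times for each tube and report the intervals by arm.

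**Section 12.2.** Code the tubes so that the laboratory does not know the arm. Include both arms in every assay run and keep each patient's visits together in one run. This is a precaution; the documents do not show that runs would otherwise be unbalanced.

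**Section 14.** State that each marker is compared between arms adjusted for its baseline value. Because adjustment removes only part of a constant handling difference (Step 5), show change from baseline alongside it if the recorded times turn out to differ by arm.

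**Cost.** Protocol wording, a draw and a freezing time on each tube (the centrifugation time can go on the same label), and a holding step for control samples, which then wait slightly longer than they need to. No extra samples are required.

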## 12. Biochemical analyzes

# 12.1- Non-specific markers

The biochemical analyzes in the blood collected from the volunteers will be performed in the laboratory of clinical analysis to be contracted. The following tests will be performed: Hemogram, C-reactive Protein and erythrocyte sedimentation rate.

## 12.2- Specific markers

For the study of osteoarthritis, IL-1 $\beta$ , IL-6, IL-8, IL-17, TNF- $\alpha$  and TGF- $\beta$  are considered as classic biomarkers. These cytokines will be quantified in serum samples obtained from patients by the Cytometric Bead Array (CBA) technique (BD Bioscincts Pharmigen, San Diego, CA, USA). The CBA assay allows multiple cytokines present in serum, plasma or even culture supernatants to be separated and quantified by cytometry using a single fluorophore. Samples after being labeled will be read by Flow Cytometry using the BD FacsCalibur cytometer, the results obtained will be analyzed by FCAP Array Software V3.0 (BD Bioscinces Pharmigen, San Diego, CA, USA). The results obtained after analysis will be expressed in pg / mL. The tests and analyzes will be carried out in partnership with the Laboratory of Cellular and Molecular Immunology of the Infectious Diseases Nucleus (NDI), located at the Federal University of Espírito Santo (UFES).

## 13. Clinical evaluation and follow-up of volunteers

The clinical evaluation and application of the questionnaires in the patients will be made by an expert advised of undergraduate students properly trained for the application of the questionnaires and of potential alarm signals.

### 13.1 Visual Analog Scale

It consists of a graduated scale of 0 to 10 with regular intervals where zero means absence of pain and 10 is the maximum pain already experienced by the patient.

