#### 10. Values evaluated

# 10.1 Primary outcome Measure:

Change pain perception through the visual analgesic scale of the volunteers (VAS)

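### The top of the primary pain scale is each patient's own worst pain to date, so scores are unevenly scaled and can change while the knee does not

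*Combined protocol and SAP*

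**What the plan says.** Section 13.1 holds the only definition of the scale in the supplied text: a graduated 0 to 10 scale on which "zero means absence of pain and 10 is the maximum pain already experienced by the patient". Section 10.1 makes change on this scale the primary outcome.

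Under section 9 the questionnaires are "repeated at the beginning of the study (day zero) and after 1, 2, 3, 6, 9 and 12 months", which is seven assessments. The same section refers to Annex C for the form, and that annex is not in the supplied text. It also says that selected patients "will have their knee (s) affected by OA fully submerged in the beach sand", so one or both knees may be involved. Neither section 10.1 nor section 13.1 says which knee is rated or over what period.

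Section 3 sizes the trial on a difference of at least 3 points on this scale, "considering a significance level of 1% and test power of 95% in two-tailed hypothesis test", with "the value of 4 for standard deviation". It arrives at 126 patients before allowance for loss. Nothing in the supplied text holds the meaning of 10 at what it was on day zero.

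**The concern.** A change score needs the same ruler at every visit, and a target difference in points needs roughly the same ruler in every patient. The worst pain a patient has had so far provides neither. It differs between patients with the same knee pain, it may come from another part of the body, and it is replaced whenever something worse happens.

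Three things follow from the wording alone:

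- **Ceiling.** If the current knee pain is the worst ever, the patient starts at 10. If the knee then gets worse, the new pain becomes the new 10, and the score does not move.
- **Drift.** With the knee unchanged, a new worst pain from any cause lowers the score. Drift of this kind goes only one way and looks like improvement.
- **Uneven units.** One point stands for a different amount of pain in different patients, although section 3 treats 3 points as one quantity.

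At stake are the precision and the interpretation of the primary outcome, and above all any statement about change from baseline within an arm.

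**Working it through.** **1. The plan's own figure.** The inputs from section 3 are difference 3, SD 4, two-sided alpha 0.01 and power 95%. For two means:

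n per arm = 2 × [4 × (2.576 + 1.645) / 3]² = 63.34

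This rounds up to 64 per arm, or 128 in total. The stated 126 is 63 per arm, where power is 94.9%. The figure reproduces to within 2 patients, and the anchor changes none of its inputs.

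**2. A model of the anchor (an assumption).** Let P be knee pain and W the worst pain so far, both on an imagined fixed intensity scale. Reading section 13.1 as strict ratio scoring gives score = 10 × P / W. The documents give no values for P or W, so steps 3 to 6 are illustrations.

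**3. Drift within a patient, with P constant at 6.**

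| W before | W after | Score before | Score after | Change |
|---|---|---|---|---|
| 8 | 10 | 7.5 | 6.0 | −1.5 |
| 6 | 8 | 10.0 | 7.5 | −2.5 |
| 10 | 10 | 6.0 | 6.0 | 0 |

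The first row is half of the 3-point target (1.5 / 3). The last row is a patient who has no new worst pain during the year, and nothing happens to that score.

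**4. Ceiling.** If P = W = 6, the score is 10 × 6/6 = 10. If the knee worsens to 8, then W is also 8 and the score is 10 × 8/8 = 10. A 2-unit worsening is recorded as no change.

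**5. Uneven units.** A 2-unit fall in pain scores 10 × 2/W, which is 3.3, 2.5 or 2.0 points for W = 6, 8 or 10. Conversely, 3 points stand for 3 × W/10, which is 1.8, 2.4 or 3.0 units.

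**6. Cost as noise.** Suppose drift adds independent noise with SD s to the planned SD of 4, so that the total SD is √(16 + s²).

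| s | Total SD | Total N for 95% power | Power at 63 per arm |
|---|---|---|---|
| 0 | 4.00 | 128 | 94.9% |
| 0.5 | 4.03 | 130 | 94.5% |
| 1 | 4.12 | 136 | 93.4% |
| 2 | 4.47 | 160 | 88.3% |

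The documents do not say which row applies.

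**The case against.** The strongest reply is that the instrument itself has not been seen. Section 13.1 is a one-sentence description, and Annex C, the form patients read, may print a different top anchor, a named knee and a recall period. This stands as a limit on confidence. It cannot be asserted that the trial has no knee or recall rule, only that the supplied text shows none. Section 13 also has trained people apply the questionnaires, who may direct the patient to one knee. It does not remove the point, because if Annex C differs from section 13.1 the two need reconciling.

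Second, worst pain imaginable is subjective too, and every bounded scale has a ceiling. That is true, and the gain is one of degree. An anchor that does not refer to past pain is not redefined by its own wording each time a worse pain occurs, and it does not by definition place a patient at the top because today's knee pain is the worst so far.

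Third, patients are aged 30 to 95 (section 5), so the anchor moves only if a lifetime record is broken within twelve months. That may be uncommon. It limits the drift, but it does not affect the uneven units or the patient who starts at 10.

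Fourth, a reader might infer that the anchor makes the sand treatment look effective, since drift with a constant knee always resembles improvement. The documents do not support this. The trial is randomised (section 1), and drift that is equal in both arms does not by itself bias the between-arm difference. Bias needs new worst pain to occur unequally, and nothing in the documents shows that it would.

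**Conclusion.** The point holds as a weakness in the definition of the primary measurement. As worded, the scale depends on pain history, is not limited to the knee, and has a top that can only move upward. For the randomised comparison the main consequences are noise and uneven scaling, with bias only under unequal occurrence of new worst pain. Within-arm change is exposed directly.

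Its size is unknown. A reader might take 1.5 points as the expected error, but that figure rests on ratio scoring, a constant pain of 6 and a rise in worst pain from 8 to 10, none of which is in the documents. A reader might also infer that the sample size is wrong, but it reproduces and no corrected number follows. As noise, the loss of power is slight for an assumed added SD of 0.5 or 1, and notable only at 2. The case for acting is that the remedy costs very little and concerns the primary outcome. Confidence is limited by the absence of Annex C from the supplied text.

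**What to change.** Reword section 13.1 and reconcile it with Annex C so that both carry the same text:

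- One top anchor that does not refer to the patient's past pain, for example 10 = worst pain imaginable.
- One knee to be rated, designated for each patient at day zero and kept for every visit. How it is chosen when both are affected is for the sponsor to decide.
- One stated recall period. Its length is also the sponsor's choice.
- The same printed wording at all seven assessments in both arms.

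The cost is one paragraph and a reprinted form, with no extra visits, staff or patients. If enrolment has begun, patients already enrolled should keep the wording they started with to the end, and the form version should be recorded for each patient, so that no change score mixes two anchors. Any report of within-arm change for patients on the present wording should state the anchor that was used.
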